5.1 Imputation rules

5.1.1 Study treatment

Missing/partial start date or end date of study treatment will not be imputed.

5.1.2 AE date imputation

Rules for imputing AE end date or start date will be provided in Programming Dataset Specification (PDS) document in details.

5.1.3 Concomitant medication date imputation

Rules for imputing the CM end date or start date will be provided in Programming Dataset Specification (PDS) document in details.

5.2 AEs coding/grading

The MedDRA version which will be available at the time of database lock, will be used for the coding purpose of the adverse events.

5.3 Data pooling and assessment windows

Data from unplanned or unscheduled visits or the early treatment/study discontinuation visits will be listed, as appropriate. For patients who do not complete the study treatment, the treatment discontinuation visit will be an unscheduled visit.

Clinical laboratory measurements, vital signs and ECG data from unplanned or unscheduled visits will only be included in the summaries of the notable values. All efficacy data from these visits will not be used for missing data imputation unless specified otherwise.

Laboratory, vital signs, and ECG values that have complete date and time values will be slotted into pre- or post-dose assessment based on the actual date/time. For values with missing date/time, scheduled visit date and time will be used. This rule will be applied to data from scheduled visits only. If a measurement scheduled as pre-dose is actually performed post-dose, or vice versa, the data will not be used for by time point assessments.

5.4 Laboratory parameters – definition of clinically notable values

The following table shows the criteria for clinically notable laboratory values. Not all parameters have notable criteria defined.

Laboratory parameter (unit)	Bound for notably low values	Bound for notably high values
Hematology		
Hematocrit (v/v)		
Male 6-12	0.31	
Female 6-12	0.31	
Hemoglobin (g/L)		
Male 6-12	97	
Female 6-12	92	
Thrombocytes (x10E9/L)	75	500
WBC's (x10E9/L)	2.8	16.0
Chemistry		
Alkaline Phosphatase (IU/L)	-	3xULN
Total Bilirubin (µmol/L)	-	34.2
Creatinine (µmol/L)		105
Potassium (mmol/L)	3	6
Glucose (mmol/L)	2.78	9.99
ALT/SGPT (U/L)	-	3 x ULN
AST/SGOT (U/L)	-	3 x ULN
BUN/ Urea (mmol/L)		9.99
Sodium (mmol/L)	125	160
Gamma GT (U/L)		3 x ULN
v = volume, ULN = upper limit of normal		

5.5 Vital signs and ECG – definition of clinically notable values

The following table shows the clinical notable criteria for vital signs.

Vital sign parameter (unit)	Lower bound of clinically notable range	Upper bound of clinically notable range
Notable value considering newly occurring or worsening cases		
Systolic blood pressure (mmHg)	< 80 (all)	> 150 (all)
Diastolic blood pressure (mmHg)	< 45 (all)	> 105 (all)
Pulse rate (bpm)	< 50 (all)	> 150 (6-8), >130 (9-12)
Notable change from baseline		
Systolic blood pressure (mmHg)	≤ 90 and decrease from baseline by ≥ 15	≥ 140 and increase from baseline by ≥ 15
Diastolic blood pressure (mmHg)	≤ 55 and decrease from baseline by ≥ 15	≥ 95 and increase from baseline by ≥ 15
Pulse rate (bpm)	≤ 60 and decrease from baseline by ≥ 15	≥ 140 and increase from baseline by ≥ 15 (6-8) ≥ 120 and increase from baseline by ≥ 15 (9-12)

The following table shows the clinical notable criteria for QTcF.

ECG parameter (unit)	Clinically notable range
Notable value criterion for newly occurring or worsening cases	
QTc (msec)	> 450 msec for males and females
QTc (msec)	> 500 msec for males and females
Notable change from baseline	
QTc	30 – 60 msec
QTc	> 60 msec

5.6 Statistical methodology and assumptions

Not applicable as no inferential analyses will be conducted.

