## **4 Rationale**

### **4.1 Rationale for study design**

This is an open-label study with an 8 day preferred treatment period to assess pharmacokinetics and safety of 2 different doses levels of fevipiprant CT. The 2 dose cohorts (A and B) will be studied consecutively, to allow to assess low dose data before escalating to a higher dose level in this first study in children of 6 to < 12 years. After cohort A an interim analysis will decide the fevipiprant dose and number of subjects tested in cohort B. By this a sufficiently good definition of the primary pharmacokinetic endpoint and an adequate exposure in the high dose group is supported. As the primary objective of the study is a pharmacokinetic assessment, the open-label design is considered appropriate. A population pharmacokinetics (PopPK) modeling approach will be used to integrate data from this study with adult and adolescent PK data to support the pediatric Phase III dose selection. The PK sampling in this study (i.e. from pre-dose to 8 h post dose at steady state) is adequate to inform the PopPK model. This is the first fevipiprant study in this age range and final dose selection requires the data obtained in this study. Therefore, pediatric Phase III dose level may not be identical to one of the dose levels tested in this study. However, the flexibility in selecting the high dose based on 75 mg/day data will allow an appropriate range to be covered.

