#### **4.4 Purpose and timing of interim analyses/design adaptations**

A planned interim analysis will be conducted to support decision making when 6 subjects (3 subjects from each of the 2 age strata) receiving the 75 mg dose level complete the treatment and provide the planned PK and safety data. At interim analysis, safety, as well as mean and variability of PK data of the 75 mg dose level will be assessed to have the right dose and number of subjects for the higher dose at the second stage.

For detailed information, please refer to [Section 12.7](#). Once PK data from 6 children are available, an interim analysis will be performed using non-compartmental methods and based on protocol times (e.g. preliminary PK data).

Additional interim analysis may be conducted when at least 6 subjects on high dose will complete the treatment (in case where sample size on high dose is adjusted to be more than 6 after first interim analysis) and the sample size of high dose can be refined based on emerging PK data.

The flexibility to adapt the sample size and dose of the high dose cohort based on mean and variability of PK data at the low dose will ensure that the primary endpoint of this study is met supporting pediatric dose selection for Phase III. The Phase III dose selection will apply population PK methodology and combined analysis with PK data from other age strata. The non-compartmental analysis performed in this study is considered adequate to ensure sufficiently good definition of key PK properties to inform the population PK model.

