### **12.4.2 Statistical model, hypothesis, and method of analysis**

The primary variables, AUC0-24h,ss, Cmax,ss and CL/F will be analyzed by standard non-compartmental analysis and summarized by cohort through descriptive summary statistics (including mean, SD, CV% mean, Geometric mean, CV% geometric mean, median, minimum and maximum). Additionally, CL/F will also be summarized across cohort.

Plasma concentrations will be assessed at the EOT Visit (pre-dose, 0.5, 1, 2, 3, 5, 8h) and will be expressed in mass per volume units. All concentrations below the lower limit of quantification (LLOQ) or missing data will be labeled as such in the concentration data listings. Concentrations below the limit of quantification will be treated as zero in summary statistics

and for the calculation of parameters and the pre-dose concentration on the EOT Visit will also be used as 24 h concentrations to derive AUC0-24h,ss.

PK data from this study will be analyzed together with PK data from other studies in adult subjects using a population pharmacokinetic modeling approach with the aim to support dose selection for pediatric phase III studies. The modeling approach will be specified in a separate analysis plan and results will be reported separately from the CSR.

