## 12.7 Sample size calculation

### 12.7.1 Primary endpoint(s)

Sample size is guided by statistical precision and requirements for pharmacokinetic data from pediatric subjects for inclusion in population PK modelling. Based on exploratory optimal design evaluation using modeling and simulation techniques, at least 12 subjects is expected to be sufficient for a pooled population PK analysis which is planned to be used to support dose selection for pediatric phase III studies. Since adult data on fevipiprant does not show a clinically relevant deviation from dose proportionality, data from the low and high dose cohort are equally valuable to inform the population PK model. Drop-outs and non-completers will be replaced.

At first stage it is required to have PK data from 6 subjects receiving 75 mg dose to assess safety, as well as mean and variability of PK data to enable at the second stage to have the right dose and number of subjects. Moreover, data from 6 subjects will provide ~80% probability for acceptable precision in calculating the geometric mean. More specifically, the inclusion of 6 subjects would result in the 95% confidence interval (CI) of the geometric mean of QAW039 AUC0-24h,ss being in the range of (68%U, 147%U). U is the observed geometric mean, assuming a coefficient of variation of 31% based on data from previous study ([QAW039A2111] study). This level of precision balances needs for reliable parameter estimation and clinical feasibility and is in agreement with guidance provided by health authorities. (General Clinical Pharmacology Considerations for Pediatric Studies for Drugs and Biological Products, FDA).

An interim analysis will be conducted when 6 subjects (3 subjects from each of 2 age strata) receiving the 75 mg dose will complete the treatment and provide the planned PK samples. At interim analysis, the following outcomes are foreseen based on AUC0-24h,ss:

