2.5.2 Statistical hypothesis, model, and method of analysis

The primary variables, AUC_{0-24h,ss}, C_{max,ss} and CL/F will be analyzed by standard non-compartmental analysis and summarized for Cohort A, through descriptive summary statistics (including mean, SD, CV% mean, Geometric mean, CV% geometric mean, median, minimum and maximum).

Plasma concentrations will be assessed at EOT visit (pre-dose, 0.5, 1, 2, 3, 5, 8h) and will be expressed in mass per volume units. All concentrations below the lower limit of quantification (LLOQ) or missing data will be labeled as such in the concentration data listings. Concentrations below the limit of quantification will be treated as zero in summary statistics and for the calculation of parameters and the pre-dose concentration on EOT visit will also be used as 24 h concentrations to derive AUC_{0-24h,ss}.

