2.7 Interim analysis

A planned interim analysis will be conducted to support decision making when 6 subjects (3 subjects from each of the 2 age strata) receiving 75 mg dose complete the treatment. The interim analysis will be performed based on preliminary PK data e.g. protocol times can be used to calculate PK parameters. At interim analysis, based on PK data from the 75 mg dose level the high dose will be chosen.

For detailed information, please refer to [Section 3](#).

3 Sample size calculation

Sample size is guided by statistical precision and requirements for pharmacokinetic data from pediatric subjects for inclusion in population PK modelling. Based on exploratory optimal design evaluation using modeling and simulation techniques, at least 12 subjects is expected to be sufficient for a pooled population PK analysis which is planned to be used to support dose selection for pediatric phase III studies. Since adult data on fevipiprant does not show a clinically relevant deviation from dose proportionality, data from the low and high dose cohort are equally valuable to inform the population PK model. Drop-outs and non-completers will be replaced.

At first stage it is required to have PK data from 6 subjects receiving 75 mg dose to assess safety, as well as mean and variability of PK data to enable at the second stage to have the right dose and number of subjects. Moreover, data from 6 subjects will provide ~80% probability for acceptable precision in calculating the geometric mean. More specifically, the inclusion of 6 subjects would result in the 95% confidence interval (CI) of the geometric mean of QAW039 AUC_{0-24h,ss} being in the range of (68%U, 147%U). U is the observed geometric mean, assuming a coefficient of variation of 31% based on data from previous study (QAW039A2111 study). This level of precision balances needs for reliable parameter estimation and clinical feasibility and is in agreement with guidance provided by health authorities. (General Clinical Pharmacology Considerations for Pediatric Studies for Drugs and Biological Products, FDA).

An interim analysis will be conducted when 6 subjects (3 subjects from each of two age strata) receiving the 75 mg dose will complete the treatment and provide the planned PK samples. At interim analysis, the following outcomes are foreseen based on AUC_{0-24h,ss}:

In terms of exposure i.e. mean AUC_{0-24h,ss}:

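### Should the SAP list the 95% confidence interval of the geometric mean AUC0-24h,ss that helped to size Cohort A?

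*SAP*

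**What the plan says.** Protocol 12.7.1 and SAP 3 give several reasons for six children in the first cohort. One is to supply data for population PK modelling. Another is "to assess safety, as well as mean and variability of PK data", to guide the second stage. A third is precision: both sections say that "the inclusion of 6 subjects would result in the 95% confidence interval (CI) of the geometric mean" of AUC0-24h,ss falling within 68% to 147% of the observed value, with about 80% probability, assuming a CV of 31%.

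The planned output is descriptive. Protocol 12.4.2 has the primary variables "summarized by cohort through descriptive summary statistics (including mean, SD, CV% mean, Geometric mean, CV% geometric mean, median, minimum and maximum"). SAP 2.5.2 repeats the list for Cohort A: "descriptive summary statistics (including mean, SD, CV% mean, Geometric mean, CV% geometric mean, median, minimum and maximum"). Neither list names n or a confidence interval, and neither document writes a formula for the geometric CV. For the AUC itself, SAP 2.5.2 says that "the pre-dose concentration on EOT visit will also be used as 24 h concentrations".

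SAP 5.6, where statistical methodology would be set out, reads "Not applicable as no inferential analyses will be conducted". SAP 1 and 2.5.1 explain the setting: the sponsor ended the study early, all Cohort A patients completed, and Cohort B has no PK data.

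**The concern.** A quantity that helps to justify a sample size would normally be expected in the results. Here the CI appears in the sizing section and nowhere in the outputs. Cohort A is the whole primary result, so a reader would see a geometric mean without its interval.

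Rebuilding the interval needs two things that the SAP does not spell out:

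- **The number of AUC values.** SAP 2.3.1 tabulates the size of each analysis set. One valid concentration can admit a child to the PK set (SAP 2.2), whereas AUC0-24h,ss also needs the pre-dose value as its 24 h point.
- **The definition of the geometric CV.** More than one formula is conceivable.

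The protocol's language can also be read as a promise of precision. Section 4.4 says that the adaptive flexibility "will ensure that the primary endpoint of this study is met supporting pediatric dose selection for Phase III", and section 4.1 says that "a sufficiently good definition of the primary pharmacokinetic endpoint and an adequate exposure in the high dose group is supported". No section says how either would be judged.

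**Working it through.** **Inputs** (protocol 12.7.1, SAP 3): n = 6, CV = 31%, 95% two-sided CI, target 68% to 147%, probability about 80%. The observed geometric CV is not in the documents, so the observed intervals below are illustrations.

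**1. The plan's own figure.**

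- Log-scale SD: s = sqrt(ln(1 + CV²)) = sqrt(ln 1.0961) = 0.3029.
- The 80th percentile of the sample SD is sqrt(s² × chi2(0.80, 5)/5). The limits are exp(± t × that SD/√6) with t(0.975, 5) = 2.5706, which gives **68.1% to 146.8%** (stated: 68% to 147%).
- The largest sample SD that keeps the CI within 147% is ln(1.47) × √6/2.5706 = 0.3671. So P(within) = P(chi2 with 5 df ≤ 5 × 0.3671²/ln 1.0961) = **0.804**, and P(outside) = 1 − 0.804 = 0.196.

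**2. Which CV formula the plan uses.** The same calculation with n − 1 degrees of freedom was applied to the 120 cells of the sizing table (N = 7 to 18, CV 35% to 80%).

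| Relation between CV and s | Cells reproduced within 1 point |
|---|---|
| CV = sqrt(exp(s²) − 1) | 120 of 120 (largest difference below 0.6) |
| CV = s | 8 of 120 |
| CV = exp(s) − 1 | 0 of 120 |

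The definition is unwritten, but the SAP's own table identifies it.

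**3. The interval from the planned outputs.** Given the geometric mean, the geometric CV and n, the CI is GM × exp(± t × s/√n). At n = 6:

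| Observed geometric CV | s | Factor | 95% CI, % of geometric mean |
|---|---|---|---|
| 31% | 0.303 | 1.374 | 73% to 137% |
| 35% | 0.340 | 1.429 | 70% to 143% |
| 40% | 0.385 | 1.498 | 67% to 150% |

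The CI stays within the planning range up to a geometric CV of sqrt(exp(0.3671²) − 1) = 38.0%.

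**4. Whether n is really in doubt.** The number of AUC values is a result, which a SAP cannot state in advance. The documents point to six:

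- All Cohort A patients completed (SAP 1).
- Children not eligible for PK assessment are replaced (SAP 1.1).
- The interim analysis calls for six children who supply the planned samples (SAP 3). Cohort B was to open only after Cohort A's safety and available PK data had been assessed (protocol 6.3.2), and five Cohort B children were treated (SAP 1).
- Deviations affecting PK exclude a child from the PK set (SAP 2.2), as does failing to take four consecutive daily doses (SAP 5.7). This narrows the gap between that set and the number of AUC values.
- A pre-dose value below the quantification limit counts as zero (SAP 2.5.2), so it still yields an AUC. A missing one would be labelled in the planned concentration listing and easily seen among six children.

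**5. What depends on the interval.** The Cohort B dose rule uses mean AUC0-24h,ss and the Cohort B size rule uses its CV% (SAP 3). Neither uses an observed CI, and Cohort B has ended. Phase III dose selection was assigned to population PK (protocol 4.4) under a separate analysis plan (protocol 12.4.2).

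**6. The two protocol sentences.** In section 4.4 the subject of the sentence is the freedom to adapt the dose and size of the high-dose cohort. In section 4.1 the sentence follows directly from the interim decision on Cohort B. Neither promises a precision result for Cohort A.

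**The case for a change.** The best case for a change is that it costs almost nothing. A count, one interval and a footnote in an existing table would show directly the precision that the sizing section talks about. The abbreviated SAP does not explain the omission, since the full protocol list lacks the CI too. An open-ended list permits these items without committing anyone to them. The inputs also have some effect. With five AUC values instead of six, the CI at a geometric CV of 31% would be 69% to 146% rather than 73% to 137%. If the output used exp(s) − 1, a printed 40% would mean 70% to 142% rather than 67% to 150%.

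It stands that the CI is unlisted, that the formula is unwritten, and that printing both would be good practice. The rest carries little weight. Nothing in the documents supports exp(s) − 1, and the sizing table rules it out as the plan's definition. Five AUC values would require a loss of which there is no sign. A sizing calculation based on precision does not oblige a descriptive plan to print the same interval, and SAP 5.6 agrees with SAP 2.5.2, which contains no inference. Setting the observed CI beside 68% to 147% would also carry a risk. The range is a planning bound, not a success criterion, and SAP 3 accepts missing it at a CV of 80%. Even with a true CV of 31%, the CI would fall outside in 19.6% of cases and could be misread as a failure.

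**Conclusion.** No change follows. This is a reporting detail that analysts fill sensibly. The plan as written gives a sound geometric mean and geometric CV for Cohort A, and the 95% CI follows from them by one line of arithmetic. Printing it would leave every estimate, dose rule and sample size as it is. For scale, the interval is 73% to 137% of the geometric mean at a geometric CV of 31% and 67% to 150% at 40%.

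The conclusion assumes six AUC values, which the documents make very likely but do not state. It also assumes that the output uses the log-normal CV definition behind the sizing table. A sponsor who wishes to help the reader could print n, the t-based log-scale interval and a footnote with that definition, labelled as estimation; the analysis does not depend on it.

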5.7 Rule of exclusion criteria of analysis sets

The following table provides the protocol deviations (PD) and other criteria leading to partial or complete exclusion from analyses sets

Deviation ID	Description of Deviation
Deviations leading to exclusion from all analyses sets	
INCL02A	Subject entered the study without the parent/legal guardian signing the informed consent
INCL02B	Subject entered the study without signing the assent where local law requires assent
Deviations leading to exclusion from PK analysis set	
TRT01	Subject did not receive a total of at least four consecutive, daily doses of study drug

6 Reference

General Clinical Pharmacology Considerations for Pediatric Studies for Drugs and Biological Products, FDA
